7.3 Secondary endpoints analysis

7.3.1 Response at Month 6 on SRI-4

The composite endpoint (SRI-4 response at Month 6) is a binary endpoint based on three variables, as defined below.

The mSLEDAI-2K score is derived on the mSLEDAI-2K eCRF page for every visit and can be used without further derivation. The PGA data is taken from the Physician’s Global Assessment (PGA) eCRF page.

A time windowing approach, as defined in Section 5.4.4, is applied for the variable derivation.

7.3.1.1 Overview of analyses

The main estimator as well as sensitivity and supplementary estimators for the secondary estimand #1 as defined in Section 3.1.1 are summarized in Table 7.

Table 7 Overview of analyses for secondary estimand #1

Estimator	Section	Endpoint	Imputation method	Analysis
Main estimator	7.3.1.5	Response on SRI-4 at Month 6	None (MAR assumption)	Repeated measurements GLMM. To ensure that the estimand based on the treatment policy strategy can be estimated, the value for the variable of SRI-4 is used regardless of occurrence of intercurrent events, such as treatment discontinuation.
Sensitivity estimator #1	7.3.1.6.1	Response on SRI-4 at Month 6	None (MAR assumption)	Repeated measurements GLMM based on PPS.
Sensitivity estimator #2	7.3.1.6.2	Response on SRI-4 at Month 6	MI assuming MAR	Repeated measurements GLMM on complete data imputed using MI assuming MAR.
Sensitivity estimator #3	7.3.1.6.3	Response on SRI-4 at Month 6	MI assuming MNAR (tipping point)	Repeated measurements GLMM on complete data imputed using MI assuming MNAR.
Supplementary estimator #1 (response over time)	7.3.1.6.4	Response on SRI-4 at Month 1, 2, 3, 4, 5 and 6	None (MAR assumption)	Repeated measurements GLMM.
Supplementary estimator #2 (subgroups)	7.3.1.7	Response on SRI-4 at Month 6	None (MAR assumption)	Subgroup analyses.

GLMM = generalized linear mixed model; MAR = missing at random; MI = multiple imputation; PPS = Per-Protocol Set; SRI = Systemic Lupus Erythematosus Responder Index.

7.3.1.2 Variables

The three variables are defined as follows:

mSLEDAI-2K Responder

The absolute change of the mSLEDAI-2K from baseline to Month 6 (using time window approach) is defined as:

$$\text{Change in mSLEDAI-2K} = \text{mSLEDAI-2K score at Month 6} - \text{mSLEDAI-2K score at baseline.}$$

Subjects with a reduction from baseline to Month 6 of ≥ 4 are considered to be responders (Responder = 1), subjects with a reduction of < 4 or an increase are considered to be non-responders (Responder = 0).

BILAG-2004 Responder

A responder (1) is defined as having no new BILAG A organ domain score and at most one new BILAG B organ domain score assessed for the nine body systems. A responder can only be assessed if the full information of all body systems is available.

Non-responders (0) are defined as having one or more new BILAG A organ domain scores or at least two or more BILAG B organ domain scores. In the event of incomplete data in at least one of the body systems, but sufficient information to fulfill the non-response criteria, the subject will be considered to be a non-responder.

Subjects that fit none of the above criteria will be assigned a missing value.

PGA Responder

The absolute change of PGA from baseline to Month 6 is defined as follows:

$$\text{Change of PGA} = \text{PGA value at Month 6} - \text{PGA value at baseline.}$$

A responder (1) is a subject with an increase of ≤ 0.3 compared to baseline. A non-responder (0) is defined as having an increase of > 0.3 compared to baseline. Subjects with missing data either at baseline or Month 6 will be assigned a missing value.

Composite endpoint

A responder (1) for the endpoint SRI-4 response at Month 6 is defined as a responder of all three variables, as defined above. If at least one of the three variables indicate non-response, the subject is considered to be a non-responder (0). If at least one of the three variables is missing, the subject is assigned a missing value, unless at least one non-missing variables indicates non-response.

Data of this endpoint is derived for all monthly post-baseline visits up to Month 6.

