7 EFFICACY VARIABLES AND ANALYSES

7.1 Overview

The primary efficacy variable of the study is the absolute change of the mSLEDAI-2K score from baseline to Month 6. Changes for all time points from Month 1 through Month 6 will be derived and included in the statistical analysis model of the primary endpoint.

There are two secondary endpoints that are analyzed in hierarchical manner for each dose level comparison following any rejections of dose level comparisons hypotheses of the primary endpoint:

- Response at Month 6 on SRI-4 defined as follows:
 - Reduction from baseline of at least 4 points in the mSLEDAI-2Kand
 - No new BILAG A organ domain score and no more than one new BILAG B organ domain score compared with baselineand
 - No increase of more than 0.3 points on the PGA since baseline.
- Response (no worsening) at Month 6 on BILAG-2004 disease activity index defined as no new BILAG A organ domain score and no more than one new BILAG B organ domain score compared with baseline.

The other efficacy endpoints are described as follows:

- Response at Month 6 on the mSLEDAI-2K score defined as a reduction from baseline of at least 4 points.
- Response (no worsening and improvement) at Month 6 on BILAG-2004 disease activity index defined as follows:

- No new BILAG A organ domain score and no more than one new BILAG B organ domain score compared with baseline
- and
- Any BILAG A organ domain score at study baseline improved to B/C/D or any BILAG B organ domain score at study baseline improved to C/D.
- Response at Month 6 on SRI-5, -6, -7, -8 defined as the secondary endpoint (response at Month 6 on SRI-4) with reductions in mSLEDAI-2K of 5, 6, 7 and 8, instead of a reduction of 4.
 - Occurrence of mild, moderate and severe flares from baseline up to Month 6.
 - Time to first severe flare from baseline to Month 6 (severe flares defined as BILAG A organ domain score presence due to items that are new or worse).
 - Time to first flare from baseline to Month 6.
 - Change from baseline to Month 6 in PGA score.

Exploratory endpoints will be analyzed from baseline to a maximum of 12 months on all available assessments according to two groups:

- Group 1: All randomized subjects, for whom baseline is defined as the last available measurement before the start of randomized treatment in TP1.
- Group 2: Subjects re-randomized at Month 6, for whom baseline is defined as the last available measurement before the start of re-randomized treatment in TP2.

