Endpoints for Group 1:

- Sustained mSLEDAI-2K response defined as a reduction of at least [REDACTED]
[REDACTED]
[REDACTED]
[REDACTED]
- Change from baseline to each post-baseline assessment up to Month 12 in prednisone or equivalent dose.

Endpoints for Groups 1 and 2:

- Change from baseline to each post-baseline assessment up to Month 12 in mSLEDAI-2K score.
- Response at each post-baseline assessment on improvement in the mSLEDAI-2K score, defined as a reduction from baseline of at least 4 points.
- Response (no worsening and improvement) at each post-baseline assessment on BILAG-2004 disease activity index defined as follows:
 - No new BILAG A organ domain score and no more than one new BILAG B organ domain score compared with baseline

and

- Any BILAG A organ domain score at study baseline improved to B/C/D or any BILAG B organ domain score at study baseline improved to C/D.
- Response at each post-baseline assessment on SRI-4, -5, -6, -7, -8.
- Change from baseline to each post-baseline assessment in PGA score.
- Occurrence of flares and severe flares at each post-baseline assessment (defined as either 1 or more new BILAG A or 2 or more new BILAG B organ domain scores compared to the previous visit).
- Time to first severe flare from baseline to Month 12 (severe flares defined as BILAG A organ domain score presence due to items that are new or worse).
- Time to first flare from baseline to Month 12.

The PRO/QoL endpoints are defined as follows:

- Change from baseline to each post-baseline assessment in FACIT-Fatigue Scale score.
- Change from baseline to each post-baseline assessment in PGIS-F.
- PGIC-F score at each post-baseline assessment.
- Change from baseline to each post-baseline assessment in SF-36v2™.
- Change from baseline to each post-baseline assessment in the Lupus QoL questionnaire.

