7.3.2.2 Variables

The binary response variable of this endpoint is derived as described in Section 7.3.1.2 for the BILAG-2004 endpoint.

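### The BILAG non-responder rule leaves out *new* before BILAG B, so it overlaps the responder rule and can code subjects who have not worsened as failures

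*SAP*

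**What the plan says.** SAP section 7.1 defines the BILAG-2004 secondary endpoint, and the BILAG part of SRI-4, as "no new BILAG A organ domain score and no more than one new BILAG B organ domain score compared with baseline".

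Section 7.3.1.2 turns this into a derivation for every monthly visit up to Month 6:

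- **Code 1 (responder):** "having no new BILAG A organ domain score and at most one new BILAG B organ domain score assessed for the nine body systems". A completeness condition follows: "A responder can only be assessed if the full information of all body systems is available".
- **Code 0 (non-responder):** "having one or more new BILAG A organ domain scores or at least two or more BILAG B organ domain scores".
- **Incomplete data:** a subject with missing body systems but "sufficient information to fulfill the non-response criteria, the subject will be considered to be a non-responder".
- **Missing:** only subjects who meet neither rule.

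In the SRI-4 composite, a 0 on any one component makes the composite 0. Section 7.3.2.2 has the second secondary endpoint "derived as described in Section 7.3.1.2 for the BILAG-2004 endpoint". Section 7.4.2.1 (BILAG-1) repeats the non-responder wording for another BILAG endpoint.

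**The concern.** The code-1 rule counts new B scores. The code-0 rule counts B scores without that qualifier. The two rules are therefore not complements, and the code-0 rule does not match the endpoint in section 7.1.

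Two kinds of subject are exposed. Take someone with two B domains at baseline that are still B at the visit, and no new A or B anywhere. With all nine systems graded, this subject meets both rules and the SAP does not say which prevails. With one system ungraded, only the code-0 rule can apply, so the subject becomes a non-responder. With *new* inserted, the section's own residual clause would make the value missing, to be handled under MAR (sections 7.3.1.3 and 7.3.2.3).

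The derivation supplies both secondary endpoints in the Type I error strategy of section 7.1.1. All monthly values enter the repeated-measures model, so a wrong code at Months 1 to 5 enters as well as one at Month 6. The same text feeds SRI-5 to SRI-8 (section 7.4.3.1) and the 12-month SRI analyses (section 7.5.5.1). The copy in section 7.4.2.1 feeds the other BILAG endpoint and its 12-month version (section 7.5.4.1).

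**Working it through.** The plan states no figure to reproduce. The check is whether the rules give each possible subject exactly one code.

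**Set-up.** Classify each of the nine body systems at a visit as new A (*a*), new B (*b*), B that is not new (*p*), ungraded (*m*) or anything else (*o*), with *a + b + p + m + o* = 9.

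- Responder: *m* = 0, *a* = 0, *b* ≤ 1.
- Non-responder as written: *a* ≥ 1 or *b + p* ≥ 2.
- Non-responder with *new* inserted: *a* ≥ 1 or *b* ≥ 2.

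**Complete data (*m* = 0).** There are C(12,3) = 220 patterns.

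- Responder rule met: *b* = 0 gives 10 patterns (*p* = 0 to 9) and *b* = 1 gives 9 (*p* = 0 to 8), so 19.
- Of these, the literal non-responder rule is also met when *b* = 0 and *p* = 2 to 9 (8 patterns), or *b* = 1 and *p* = 1 to 8 (8 patterns), so 16.

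| Code | As written | With *new* inserted |
|---|---|---|
| Responder only | 3 | 19 |
| Non-responder only | 201 | 201 |
| Both | 16 | 0 |
| Neither | 0 | 0 |

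**Incomplete data (*m* ≥ 1).** There are C(13,4) − 220 = 715 − 220 = 495 patterns. The ones that change have *a* = 0, *b* ≤ 1 and *b + p* ≥ 2.

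- *b* = 0, *p* ≥ 2: C(8,2) = 28.
- *b* = 1, *p* ≥ 1: C(8,2) = 28.
- Total: 56 are coded 0 as written and missing once *new* is inserted. With exactly one ungraded system it is 14 of 165.

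**Finer classification.** If persisting A is kept as its own state, there are 715 complete-data patterns: 28 responder only, 615 non-responder only and 72 both. Inserting *new* takes the 72 to 0. Of 1,287 incomplete patterns, 168 move from 0 to missing. The ratios depend on how the states are drawn; the overlap, and its removal by the correction, do not. This second count treats A improving to B as not a new B. The conclusion does not need that, because persisting B scores alone are enough.

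**Direction of any bias (assumed values only).** Suppose a share *s* of true responders is recoded to 0. Take BILAG response of 80% on placebo and 92% on active: OR = (0.92/0.08)/(0.80/0.20) = 2.88.

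- *s* = 10% placebo, 30% active: rates 0.720 and 0.644, OR = 0.70.
- *s* = 30% placebo, 10% active: rates 0.560 and 0.828, OR = 3.78.
- *s* = 10% in both: rates 0.720 and 0.828, OR = (0.828/0.172)/(0.720/0.280) = 1.87.
- *s* = 30% in both: rates 0.560 and 0.644, OR = (0.644/0.356)/(0.560/0.440) = 1.42.

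For SRI-4 at an assumed 40% against 60% (OR 2.25), the two unequal cases give 1.29 and 3.02. Response rates can only fall, but the odds ratio can move either way.

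**The case against.** The best reply is that the intent is not in doubt. Section 7.1 and the responder sentence agree, and *new* can be read as carrying over from the A scores earlier in the same sentence. If the responder rule governs, complete-data results do not change. Harm then needs a programmer to follow one sentence against the endpoint definition. This is a fair argument about weight. It does not remove the defect: where the SAP means the word for both grades it writes it for both, as in the flare definition of section 7.1, "defined as either 1 or more new BILAG A or 2 or more new BILAG B organ domain scores compared to the previous visit". Nor does the responder rule help when data are incomplete, because it cannot then apply.

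The incomplete-data route may also be narrow. *Not gradable* is listed for the Screening summary (section 6.8.3.5.1), so applying it to later visits is an inference. Addendum section 2.4.1 has BILAG collected remotely under a procedure that accepts incomplete assessments, but the addendum is limited to affected sites and periods. Remote visits are recorded as unscheduled and are to be followed by an on-site visit. Section 5.4.4 prefers a regular visit over an unscheduled one, although arguably only as a tie-breaker. These points limit how often the route is used; they do not close it.

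Three limits stand. The pattern counts are unweighted and include implausible cases, so 16 of 19 is not a share of subjects. The unequal odds-ratio cases rest on assumed differences between arms for which the documents give no support. And a BILAG 0 alters SRI-4 only when neither of the other two components is already 0.

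**Conclusion.** The concern holds. The non-responder rule as written conflicts with the responder rule beside it and with the endpoint in section 7.1. It leaves some complete-data patterns with two codes, and it assigns 0 to some incomplete ones where worsening is not established. Because this is an operative derivation rule for both alpha-tested secondary endpoints, it should be corrected even though the intended meaning can be inferred. The primary endpoint is not affected.

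The size in subjects is unknown. As an illustration on 325/5 = 65 subjects per arm, suppose true BILAG response is 70% to 90% and 5% to 30% of responders are recoded. That would move between 65 × 0.70 × 0.05 = 2.3 and 65 × 0.90 × 0.30 = 17.6 subjects per arm. Both ranges are assumptions.

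**What to change.** In sections 7.3.1.2 and 7.4.2.1 (BILAG-1), replace the non-responder sentence with one to this effect: *A non-responder (0) has, compared with baseline, at least one new BILAG A domain score or at least two new BILAG B domain scores.*

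With complete data this is the exact complement of the responder rule, so no precedence rule is needed. With incomplete data it assigns 0 only when worsening is established, and the existing residual clause sends the rest to missing. For the meaning of *new*, the text should point to the protocol; its main body was not available for this review, so no definition is proposed here.

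The cost is a few words in two paragraphs and a check that the derivation program matches. Data collection does not change.

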7.3.1.3 Handling of missing data

Missing data will not be imputed but will be handled by the repeated measurements GLMM, assuming that the data are MAR.

A summary of the patterns of missingness from baseline up to Month 6 will be provided.

7.3.1.4 Hypothesis, statistical model and assumptions

The hypotheses for the secondary endpoint (response at Month 6 based on SRI-4) are presented in Section 7.1.1.

7.3.1.5 Analysis

This secondary endpoint will be analyzed using the FAS. Following the treatment policy estimand all data will be included in the analysis regardless of early treatment discontinuation or other intercurrent events.

A repeated measurements GLMM with the logit link function will be fitted with the secondary endpoint SRI-4 as dependent variable (from Month 1 to Month 6). The model will include the treatment group, month, the treatment group by month interaction, and the OCS and mSLEDAI-2K stratification variables (from IXRS) as fixed effects.

An unstructured (UN) covariance structure will be used for estimation of the correlation between responses measured within the same subjects across multiple months. If this analysis fails to converge, the following structures will be tested in a subsequent order until model-convergence is achieved: heterogeneous Toeplitz (TOEPH); Toeplitz (TOEP); autoregressive (AR(1)); compound symmetry (CS).

Parameters will be estimated using restricted pseudo-likelihood with Newton Raphson ridging optimization and the Kenward-Roger method for calculating the denominator degrees of freedom.

The study treatment groups will be compared against placebo at each month using ORs and 95% CIs. The main comparisons are at Month 6.

The analysis will be implemented by the following SAS[®] code:

```
proc glimmix;
  nloptions technique=nrridg;
  class subjid ocs sledai_sc treatment month;
  model response = ocs sledai_sc treatment month treatment*month / link=logit dist=bin
  ddfm=kr;
  random month / type=un subject=subjid rside;
  lsmeans treatment*month / ilink cl; /* estimates event rates */
  lsmeans treatment*month / oddsratio diff cl; /* estimates ORs */
run;
```

Data for this endpoint will be summarized descriptively and listed using the FAS.

7.3.1.6 *Supplementary/sensitivity analyses*

7.3.1.6.1 *Analyses based on PPS*

The analysis of the secondary endpoint will be repeated using the PPS.

7.3.1.6.2 *Multiple imputation under MAR*

7.3.1.6.2.1 Step 1 (imputation)

Missing monthly SRI-4 scores will be imputed using a multiple imputation method [Rubin 1987], based on a model including the treatment group, the stratification factors OCS and mSLEDAI-2K (from IXRS), and all post-baseline monthly scores up to Month 6.

Instead of imputing a single value for each missing observation, a set of values is generated from the model, resulting in as many distinct complete datasets without missing data.

More specifically, the imputations will be performed in two steps: first, ‘intermittent’ missing data (a score is missing but one or more score[s] is [are] available at following month[s]) will be first imputed by a MCMC method using a non-informative Jeffreys Prior, thus creating 100 partially imputed ‘monotone’ datasets.

MCMC assumes multivariate normality for the SRI-4 scores at subsequent visits. This assumption is not satisfied for this binary endpoint. However, if the proportion of non-monotone data is not large, this will have a limited impact on the overall results. The values imputed by the MCMC will be rounded using adaptive rounding [Bernaards 2007]. In adaptive rounding, instead of using a fixed threshold of 0.5, the threshold is based on the imputed data using a normal approximation for a binomial distribution. This threshold is defined as follows, where μ is the mean of the imputed variable (including available binary observations and imputed continuous values) computed using unrounded values and $\Phi^{-1}(\mu)$ is the z value from a standard normal distribution (inverse of the standard normal cumulative distribution):

$$threshold = \mu - \Phi^{-1}(\mu)\sqrt{\mu(1 - \mu)}$$

Values greater or equal to the threshold are rounded to 1, and values smaller than the threshold are rounded to 0.

In the second step, the remaining missing data will be imputed once in each of these 100 ‘monotone’ imputed datasets using logistic regression leading finally to 100 complete imputed datasets.

The multiple imputation procedure will be implemented by the following SAS[®] code:

```
proc mi data=h nimpute=100 seed=12345 out=h2;  
  by treatment;  
  mcmc impute = monotone chain=single nbiter=200 niter=100;  
  var ocs sledai m1 -- m6;  
run;  
  
< Round imputed values in h2, using adaptive rounding >  
  
proc mi data=h2 nimpute=1 seed=12345 out=h3;  
  by_imputation_;  
  class treatment ocs sledai m1 -- m6;  
  var treatment ocs sledai m1 -- m6;  
  monotone logistic;  
run;
```

7.3.1.6.2.2 Step 2 (analysis)

Each imputed dataset will be analyzed using the same model as for the main analysis of SRI-4 described in Section 7.3.1.5.

7.3.1.6.2.3 Step 3 (combination)

Uncertainty in the imputations will be reflected appropriately in the analysis by combining the results on each imputed dataset into one summary measure. This method has been shown to be efficient in handling missing data if the missing data mechanism is missing completely at random or MAR [Schafer 1999].

The summary results across the 100 complete datasets will be aggregated following Rubin's rule. The final estimate is the mean of the 100 per-imputation estimates and the final variance is the sum of the average within-imputation variance and $(1+1/100)$ times the between-imputation variance [Rubin 1987]. From the final point estimate and variance, the 95% CI will be determined. The corresponding p-value will be displayed.

The results aggregation as the final step of the multiple imputation procedure after analysis of the 100 complete datasets will be implemented by the following SAS[®] code:

```
proc mianalyze parms(classvar=classval)=<data from step 2 >;  
  class treatment month;  
  modeleffect treatment*month;  
  ods output parameterestimates=<result dataset>;  
run;
```

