2 STUDY DESIGN AND FLOW

2.1 Study design

This is a Phase 2b, multicenter, randomized, double-blind, placebo-controlled, parallel group study to evaluate the efficacy, safety, and tolerability of cenerimod in subjects with moderate to severe SLE.

Approximately 325 adult subjects with SLE will be randomized in a 1:1:1:1:1 ratio to placebo, 0.5, 1, 2, or 4 mg once daily of cenerimod, in addition to background SLE therapy.

Once randomized, all subjects will enter a 6-month double-blind study treatment period defined as Treatment Period 1 (TP1).

Subjects randomized to, and still receiving, placebo, 0.5, 1, or 2 mg at Month 6 will continue their study treatment up to an additional maximum of 6 months in Treatment Period 2 (TP2), for a total maximum of 12 months.

Subjects randomized to the 4 mg arm will receive study treatment at this dose for a maximum of 6 months in TP1. Afterwards, subjects in this group, still receiving this dose

at Month 6, will be re-randomized in a 1:1 ratio to placebo or cenerimod 2 mg to enter TP2 and will continue for a total maximum of 12 months

Subjects who discontinue treatment in TP1 will continue study FU, performing study assessments, up to maximum duration of 12 months.

At EOT, subjects will enter a 6-month FU period (4-month before protocol Version 5).

Treatment allocation is stratified by dose of OCS at Randomization (two strata: < 7.5 mg/day or ≥ 7.5 mg/day prednisone or equivalent), and by disease activity at Screening (with two strata: mSLEDAI-2K < 10 or ≥ 10).

The study will be conducted at approximately 180 sites in 21 countries notably from the regions of Asia Pacific, Eastern Europe, Latin America, North America, and Western Europe.

No interim analysis is planned. There will be three study analyses: the Month-6 analysis, the Month-12 analysis and the final EOS analysis. Month-6 analysis will be performed when all randomized subjects have completed TP1 or discontinued the study. Month-12 analysis will be performed when all randomized subjects have completed TP2 or discontinued the study. Final EOS analysis will be performed when all randomized subjects have completed the post-treatment follow-up period or discontinued the study.

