2.3 Study periods

2.3.1 Screening period

The screening period starts with the signing of the informed consent form and ends on the day of Randomization, before the first study drug intake. This period can last up to 60 days.

During this period, the subject's SLE background medication should be maintained stable except for OCS which should be tapered to the minimum required dose and maintained stable for at least 15 days prior to Randomization [see protocol section 5.2.2.1, [D-22.031](#)].

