5.2 Baseline

- The **‘Baseline (TP1)’** value for **efficacy and safety analyses** is defined as the last non-missing value recorded prior to first study drug intake in TP1 for each endpoint and each subject individually. For subjects that were randomized but did not take any study drug, baseline (TP1) is defined as the last non-missing value recorded up to and including the day of Randomization.
- The **‘Baseline (TP2)’** value for **efficacy and safety analyses** is defined as the last non-missing value recorded up to and including the day of re-randomization for each endpoint and each subject individually. This baseline is only defined for subjects that have been re-randomized by IXRS.

For certain datasets/analyses an **‘intra-day baseline’** is derived (e.g., ECG, vital signs). This intra-day baseline is defined as the last non-missing assessment prior to study drug intake on the corresponding day. If there is no pre-dose assessment on the day (by time and date), then the intra-day baseline is considered to be missing. The intra-day baseline is calculated for parameters that are part of the hourly measurements on the day of first study drug intake (in TP1) and the day of first study drug intake of a re-initiated subject (in TP1).

For datasets where multiple measurements exist for the selection of the baseline assessment, the definition(s) is/are provided in the corresponding sections (e.g., spirometry or ECG data).

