7.2.5 Main analysis

The primary statistical analysis will be performed using the FAS, according to the intention-to-treat approach.

The null hypotheses for the primary endpoint will be tested using an MMRM on all available changes from baseline in mSLEDAI-2K for post-baseline scores from Months 1 through 6.

The following fixed effects will be included in the model:

- Treatment group.
- Month.
- Baseline mSLEDAI-2K score.
- Treatment group by month interaction.
- Baseline mSLEDAI-2K score by month interaction (as continuous variable).
- Stratification factor OCS (from IXRS).

The stratification factor mSLEDAI-2K at Screening will not be included in the model as the continuous baseline value is already included in the model.

A restricted maximum likelihood approach in combination with the Newton Raphson Algorithm will be used.

An unstructured (UN) covariance matrix will be used to account for the correlation between repeated measurements from the same subject. If this analysis fails to converge, the following structures will be tested in a subsequent order until model-convergence is achieved: heterogeneous Toeplitz (TOEPH); Toeplitz (TOEP); autoregressive (AR(1)); compound symmetry (CS). The Kenward-Roger approximation will be used to estimate denominator degrees of freedom.

The treatment effect for each cenerimod dose vs placebo will be estimated from the LSM differences for each dose vs placebo at Month 6 and their corresponding 95% CIs.

The hypothesis tests will be based on the associated p-values at the two-sided significance level of alpha of 5%, controlling for multiplicity using the Hochberg procedure as mentioned above.

This analysis will be implemented using the following SAS[®] code:

```
proc mixed method=reml;
  class subjid ocs treatment month;
  model change = ocs sledai_bl treatment month treatment*month sledai_bl*month / ddfm=kr;
  repeated month / type = UN subject=subjid(treatment);

  slice treatment*month / sliceby=month pdiff cl;
run;
```

Efficacy data of the primary endpoint will be summarized descriptively and listed using the FAS.

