7.5.3.2 Analysis

Group 1

A repeated measurements GLMM model for binary response variables will be performed as described in Section 7.3.1.5 based on 5 treatment groups as described in Section 5.4.3.3.

Group 2

A repeated measurements GLMM model for binary response variables will be performed as described in Section 7.3.1.5. The model will be fitted including data from Month 7 up

to Month 12 and from treatment groups *Cenerimod 2 mg / Ex-4 mg* and *Placebo / Ex-4 mg*. The model will include treatment group, month, TP2 baseline mSLEDAI-2K score, treatment group by month interaction and TP2 baseline mSLEDAI-2K score by month interaction as fixed effects.

All other aspects of the model are as described in Section 7.3.1.5.

7.5.4 Response (no worsening and improvement) at each post-baseline assessment on BILAG-2004 disease activity index

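### The SRI-4 model adjusts for disease activity only through the screening stratum; adding the continuous baseline mSLEDAI-2K score would gain a little power

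*SAP*

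**What the plan says.** SAP 7.3.1.5 analyses SRI-4 from Month 1 to Month 6 with a repeated-measures GLMM. Its fixed effects are treatment, month, their interaction, and "the OCS and mSLEDAI-2K stratification variables (from IXRS) as fixed effects". The code agrees: "model response = ocs sledai_sc treatment month treatment*month / link=logit dist=bin", with `sledai_sc` listed as a class variable. By SAP 2.1 and 6.8.2.1 that variable is the screening mSLEDAI-2K score, below 10 versus 10 or above. No continuous baseline score enters.

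The primary model in SAP 7.2.5 makes the opposite choice. It has the continuous baseline score and its month interaction, and gives the reason: "The stratification factor mSLEDAI-2K at Screening will not be included in the model as the continuous baseline value is already included in the model". No reason is given for handling SRI-4 differently.

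The screening stratum and the baseline are different measurements. Of the screening period, SAP 2.3.1 says: "This period can last up to 60 days". Baseline (SAP 5.2) is the "last non-missing value recorded prior to first study drug intake in TP1 for each endpoint and each subject individually", and the visit schedule repeats the mSLEDAI-2K at Randomization.

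The exploratory Group 2 models are mixed. The mSLEDAI-2K responder GLMM (7.5.3.2) includes "TP2 baseline mSLEDAI-2K score by month interaction as fixed effects". The Group 2 SRI-4 to -8 GLMM (7.5.5.2) has only treatment, month and their interaction.

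**The concern.** An SRI-4 responder must fall by 4 or more points from the baseline mSLEDAI-2K score (SAP 7.1, 7.3.1.2), so the baseline score is part of the endpoint's definition. The SAP recognises that baseline limits what can be attained: 7.4.3.1 excludes subjects with a baseline below X from the SRI-X analyses for X of 5 to 8. If baseline predicts response within the two strata, a two-level screening value discards some of that information.

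What is at stake is modest power on the first secondary endpoint. SRI-4 is tested with Hochberg over four doses, and a dose must succeed on it before a BILAG claim can be made at that dose (SAP 7.1.1).

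**Working it through.** **No plan figure to reproduce.** The supplied documents give no SRI-4 response rates, effect size or power. They also give no SD or power for the primary endpoint; protocol section 10.5 is cited but not supplied. The sizes below therefore rest on assumptions.

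**Inputs from the SAP**
- Subjects per arm: 325 / 5 = 65 (2.1).
- Missing at Month 6: 6%, stated for mSLEDAI-2K (7.2.3) and taken here for SRI-4 as well. 65 × 0.94 = 61.1, so 61 evaluable.
- Two-sided 5%, Hochberg over four doses (7.1.1). The strictest step is 0.05 / 4 = 0.0125.

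**Assumed inputs**
- Response 40% on placebo and 60% on one dose.
- Baseline score about 10, right-skewed, with 57% in the upper stratum.
- Screening-to-baseline correlation 0.84.
- OCS strata of equal size with no effect on response.

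**Unadjusted anchor.** Power = Φ{[0.20 − z√(2 × 0.5 × 0.5 / 61)] / √[(0.4 × 0.6 + 0.6 × 0.4) / 61]} = Φ{[0.20 − z × 0.0905] / 0.0887}. This gives 60.0% at z = 1.960 (0.05) and 38.4% at z = 2.498 (0.0125).

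**Comparison.** Each of 6,000 simulated trials per scenario was fitted with two Month 6 logistic models for one dose versus placebo: treatment + OCS + screening stratum, and treatment + OCS + continuous baseline. In the first set the log-odds of response are linear in baseline. In the second, the Month 6 score is a linear function of baseline plus error (SD 4). Response is then a fall of at least 4 points with the other SRI-4 components met (probability 0.95). Power is at two-sided 0.05.

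| Scenario | Stratum | Continuous | Change (points) |
|---|---|---|---|
| OR per baseline SD 1.0 | 60.7% | 60.8% | +0.1 |
| 1.25 | 60.2% | 60.4% | +0.2 |
| 1.5 | 62.2% | 63.3% | +1.1 |
| 2.0 | 62.0% | 63.7% | +1.7 |
| 2.5 | 62.6% | 66.2% | +3.6 |
| 3.0 | 64.0% | 68.9% | +4.9 |
| Slope of Month 6 on baseline 0.2 | 64.1% | 67.2% | +3.1 |
| 0.4 | 60.3% | 62.3% | +2.0 |
| 0.6 | 59.5% | 61.0% | +1.5 |
| 0.8 | 59.3% | 59.5% | +0.2 |
| 1.0 | 61.1% | 60.6% | −0.5 |

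The Monte Carlo standard error of one power figure is √(0.6 × 0.4 / 6,000) = 0.6 points, so the single negative entry is no larger than that. At slope 1.0 the change from baseline hardly depends on baseline, and no gain is expected.

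**Further checks**
- At 0.0125 the change runs from about 0 to +4.8 points (41.8% to 46.6% at OR 3.0).
- With screening-to-baseline correlation 0.94 and OR 2.0: 62.3% to 64.8%. With rates of 35% and 55% and OR 2.0: 62.6% to 65.4%.
- Stratum and continuous score together: 63.8% at OR 2.0, against 63.7% for the continuous score alone.
- Rejection under no effect, stratum versus continuous: 5.8% versus 5.7% (OR 1.0) and 5.1% versus 5.2% (OR 2.0).
- A second single-visit simulation (61 per arm, 3,000 trials, assumed inputs) gave about +6 points at slope 0.2, +3.6 at 0.4, +2.0 at 0.6, and about 0 or −0.5 at 0.8 to 1.0.

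**The case against.** Adjusting for the randomisation strata is a standard, valid choice. A reader might infer from the contrast with 7.2.5 that the SRI-4 test is biased or its error rate uncontrolled. The documents do not support that, and the null rejection rates above show no difference. This part of the objection stands in full.

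A reader might also infer that the SAP already uses a continuous baseline in its own SRI models. It does not. Section 7.5.3.2 shows only that the authors accept such a term in a binary GLMM for mSLEDAI-2K response; the Group 2 SRI model in 7.5.5.2 has no baseline score. The comparison with 7.2.5 is the one that carries weight.

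Nor is baseline imbalance left wholly uncorrected. Allocation is stratified on the screening score and the model includes the stratum. What remains is imbalance within strata and drift between screening and baseline.

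The most substantive objection is that a single-visit logistic model is not the planned model, which has six visits, an unstructured covariance and a list of convergence fallbacks. A rough six-visit check used an exchangeable GEE, 65 per arm, 300 replicates and assumed inputs. It compared the stratum with baseline plus baseline by month and gave 54.7% to 56.3% at slope 0.4, 63.0% to 65.7% at 0.7, and 60.7% to 58.7% at 1.0. The paired Monte Carlo standard errors were 1.1 to 1.7 points. The fall at slope 1.0 lies within two standard errors and is the case where no gain is expected. Still, the month interaction has not been tested in the planned GLMM, so it should be conditional on convergence.

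Finally, an SRI-4 claim at a dose also needs success on the primary endpoint at that dose, so a gain in SRI-4 power overstates the gain in claims.

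**Conclusion.** The point holds as a minor improvement in efficiency. Under assumed inputs, the continuous baseline changes SRI-4 power by about 0 to 5 or 6 percentage points. The gain is typically 1 to 4 points when baseline predicts response moderately (OR per SD 1.5 to 2.5) and about nothing when the Month 6 score tracks baseline one-for-one. That baseline predicts SRI-4 within strata is plausible from the endpoint's definition, but the supplied documents do not show it.

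The same reasoning covers mSLEDAI-2K response (7.4.1) and SRI-5 to -8 (7.4.3). A reader might carry it to the BILAG endpoints because 7.3.2.5 and 7.4.2.2 inherit the 7.3.1.5 model. Those responses are not defined by a fall in mSLEDAI-2K, so this rationale does not reach them.

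**What to change.** Before unblinding:

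- In 7.3.1.5, add the continuous baseline mSLEDAI-2K score as a fixed effect, beside or in place of `sledai_sc`, and keep OCS. Add its month interaction, as in 7.2.5, only if the model converges.
- Make the same change in 7.4.1 and 7.4.3.
- Include the continuous baseline in the SRI-4 imputation model (7.3.1.6.2), which the tipping-point analysis reuses. Otherwise imputation would rest on the stratum while the analysis uses the finer covariate.
- State that 7.3.2.5, 7.3.2.6.2 and 7.4.2.2 keep the stratum model, since they would otherwise change by cross-reference. Say also which version the Group 1 models in 7.5.3 to 7.5.5 follow.

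One sponsor team is unblinded at the Month-6 analysis (SAP 2.1). If that has already happened, report the change as a labelled supplementary analysis.

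The cost is small. The score alone adds no net parameter if it replaces the stratum and one if it sits beside it. With the month interaction over six visits, the net addition is 1 + 5 − 1 = 5 if the stratum is replaced, or 6 if it is kept. The odds ratio becomes conditional on a finer covariate, so its target value shifts slightly. No new data are needed.
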